| 2. Has not cared for a living family member for at least the last 6 months. |
| 3. Has knowledge of another family member in the same household enrolled in the study |
| 4. Currently pregnant |
| 5. Has a pacemaker |
| 6. Lives outside of the study area |

Number of Research Participants

Directions: Indicate the target number of research participants to be accrued locally, and, if this is a multi-site study, indicate the total number of research participants to be accrued across all sites.

Based on previous research by the PI and Co-Is, we conservatively estimate that ~20% of caregivers may not meet eligibility criteria. Thus, we will screen 125 participants to obtain the desired sample of size of 100.

Special/Vulnerable Populations

1. Indicate specifically if you will include each of the following special populations by checking the appropriate box:

- Adults unable to consent**
- Minors (infants, children, teenagers)**
- Wards of the state
- Foster Children
- Pregnant Women
- Neonates
- Neonates of Uncertain Viability
- Employees of CWRU or UHHS
- Prisoners
- Illiterate Individuals
- Non-English Speaking
- University Students

None

2. If the research involves individuals that are included in a special/vulnerable population, describe the additional safeguards included to protect the rights and welfare of the individuals for each population indicated.

If family caregivers who do not speak/understand the English language come forward with interest in participating and if they meet all other study criteria, we will make accommodations for translating the study measures and intervention materials or for having an interpreter provide appropriate explanations. If an illiterate individual comes forward with interest in participating and if they meet all other study criteria, we will make accommodations to dictate the consent form and all study questions. If a caregiver is an employee or student of CWRU, the consent form identifies participation in this research study as voluntary and if they choose not to participate, it will not affect their current or future relations with the university. No caregivers unable to consent will be enrolled. Adults unable to consent are only subjects to the extent that there is any identifiable information about them collected through the caregiver. They will not be present for any interventions or interactions.

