
Following informed consent, research staff will collect detailed contact information and schedule the first data collection session. The data collection for caregivers sampled involves two structured face-to-face sessions with data collectors. Data will be collected at baseline (T1) and within one month after the 4-week intervention (T2). Measures include dementia symptoms, caregiver reactions, caregiving involvement, dementia knowledge, resourcefulness, heart rate

variability, health risks, and health outcomes, comprising the 156-item questionnaire. Demographic information will also be collected (e.g. occupation, annual income, education, and questions about the care recipient such as age, number of years diagnosed with dementia, specific diagnoses, and questions related to the participant's caring of their family member with dementia). Research assistants will encourage caregivers to respond to items displayed on an iPad/ tablet as they wish, ensuring there are no right or wrong responses. At the first data collection session, the study participant will receive a resource list for Dementia Care support and services in Cuyahoga and surrounding counties.

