Within two weeks of the first data collection session, caregivers will be randomly assigned using a computer program to one of the three interventions (usual care/ education, resourcefulness, or biofeedback). Caregivers will receive the training and perform one health self-management intervention between the T1 and T2 data collections. The education, resourcefulness training, or biofeedback training will be introduced during a single face-to-face session in the caregiver's home/other private venue via a voice-over PowerPoint presentation presented on a tablet. All 90 caregivers who receive an intervention or usual care will keep a written log for the 4-week intervention period between the first (T1) and second (T2) data collection interviews. The caregivers will receive a pamphlet on their intervention (based on the PowerPoint presentation), a tracking log, and will receive telephone, email or text follow-up (preference of the study participant) for the next 28 days while performing the intervention independently and at their convenience. Interventionists will be carefully trained by Drs. [name] and [name] during a 2-day session that will include intervention delivery, cultural diversity training, and methods for providing psychological support/referral (e.g., "first call for help") in case caregivers experience psychological or physical distress during the training session or 28-day intervention period. Interventionists will be blinded to fidelity measures and different interventionists will provide education, resourcefulness training, and biofeedback; they will keep field notes and have weekly supervision by [name].

The first data collection session involves the additional measures of Financial Stress & Resourcefulness, and the second data collection adds an Intervention Evaluation Questionnaire that will ask participants for feedback regarding the intervention they received. Participants randomized to the Resourcefulness Training will be asked to complete the RT Skills Scale as part of the Intervention Evaluation Questionnaire.

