The primary study aim (Aim #1) is to examine differences across our three groups of family caregivers of persons with dementia on caregiver health outcomes from pre- to post-intervention. The underlying analyses for A1 are built around the repeated measures analysis of variance (RMANOVA). The primary analysis will be a three group × two time waves RMANOVA. These analyses will compare the three groups: 1) usual care (education), 2) resourcefulness, and 3) biofeedback across two time waves of health risks and physical and mental health outcomes. When using RMANOVA, one not only assesses mean differences across time, but also group differences and the interaction of time × group, which will allow us to test the trend of the means over time across the three groups. The RMANOVA, not only is used to determine if there are mean differences across the two time periods, it also uses orthogonal polynomial contrasts to determine linear trends of the means across time. Orthogonal polynomials are weights assigned to each time period that models a linear trend. RMANOVA will determine if these trends in the means are significant. A linear trend is indicated if there is a steady increase or decline in scores from the first time wave to the second time wave.

The second aim (Aim #2) identifies the responses to usual care (education), resourcefulness training, and biofeedback separately on the three health outcomes between the caregivers of persons with dementia sampled within the proposed administrative supplement with the caregivers of persons with bipolar disorder sampled in the parent study. This aim involves three separate analyses to compare the two groups of caregivers within each of the three treatment groups (education, resourcefulness training, and biofeedback) for each of the three health outcomes. For each intervention/treatment program, a two group by two time point RMANOVA will be used to determine differences within and between groups and the interaction of time × group. For example, one RMANOVA will examine differences between caregivers of persons with dementia and caregivers of person with bipolar disorders on health risks over two time points.

The third study aim (Aim #3), to explore differences between the two groups of caregivers in terms of their need for intervention (determined by baseline cut scores on study measures) and

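### The primary Aim 1 repeated-measures ANOVA tests raw change from T1 to T2; adjusting T2 for T1 would give a more precise comparison from the same data

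*Combined protocol and SAP*

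**What the plan says.** The Data Analysis Plan sets the primary Aim 1 analysis in one sentence: "The primary analysis will be a three group × two time waves RMANOVA". It compares education, resourcefulness training and biofeedback "across two time waves of health risks and physical and mental health outcomes". The part that carries the treatment comparison is "the interaction of time × group, which will allow us to test the trend of the means over time across the three groups". The plan also mentions main effects of time and group and a linear polynomial contrast. No covariate, ANCOVA or other baseline adjustment appears there or elsewhere in the document, so T1 enters only as the first repeated measure.

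Study Design/Procedures gives two waves: T1 at baseline, and T2 within a month after the four-week intervention. Assignment comes after T1: "Within two weeks of the first data collection session, caregivers will be randomly assigned using a computer program to one of the three interventions".

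On numbers, Study Design/Procedures says "All 90 caregivers who receive an intervention or usual care will keep a written log", while Number of Research Participants says "we will screen 125 participants to obtain the desired sample of size of 100". The plan gives no power calculation, significance level, effect size, SD or T1–T2 correlation.

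**The concern.** With two waves, a repeated-measures ANOVA without covariates reduces its time × group test to a comparison of mean raw change. Raw change subtracts the whole of the T1 score, which is the best weight only if the regression of T2 on T1 has slope 1. When the slope is below 1, subtraction carries T1 noise into the comparison. ANCOVA estimates the slope. Because assignment is random, both methods estimate the same treatment effect.

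The other terms in the model do not help. The group main effect averages T1, where no treatment effect can exist, with T2, so it halves the effect.

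At stake is power in a trial of about 30 caregivers per arm. No power analysis is given, so nothing shows that there is power to spare.

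**Working it through.** **Inputs.** From the documents: three arms, two waves, T1 before assignment, and 90 caregivers (30 per arm) or 100 (33.3 per arm). The only planned figure that can be reproduced is the screening number: 100 / (1 − 0.20) = 125, which agrees. The target of 100 cannot be reproduced, because no inputs are given.

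Assumed here: equal allocation, two-sided 5%, T1–T2 correlation ρ from 0.3 to 0.8, equal SD at both waves and no missing data. Equal SD is relaxed in step 5.

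**Step 1: equivalence.** On a simulated three-arm, two-wave data set, the RMANOVA time × group F and the one-way ANOVA F on T2 − T1 were both 1.6858.

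**Step 2: variance per person, in units of the outcome variance.**
- Raw change: 2(1 − ρ)
- T2 adjusted for T1: 1 − ρ²
- Ratio, adjusted to change: (1 + ρ)/2, so the cut is (1 − ρ)/2

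At ρ = 0.3 the ratio is 0.91/1.40 = 0.65. At ρ = 0.8 it is 0.36/0.40 = 0.90. Estimating the slope multiplies the adjusted variance by 1 + 1/(3n − 5), which is 1 + 1/85 = 1.012 at n = 30 per arm. The caregivers that the change analysis needs to match 90 under ANCOVA are 90 × 2(1 − ρ) / [(1 − ρ²) × 1.012].

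| ρ | Cut in variance | Cut net of slope cost, 30 per arm | Caregivers needed by change analysis to match 90 |
|---|---|---|---|
| 0.3 | 35% | 34% | 137 |
| 0.5 | 25% | 24% | 119 |
| 0.6 | 20% | 19% | 111 |
| 0.7 | 15% | 14% | 105 |
| 0.8 | 10% | 9% | 99 |

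**Step 3: power and detectable difference.** As an illustration, let both active arms differ from education by 0.6 SD. The between-arm sum of squares is n × (0.16 + 0.04 + 0.04) = 0.24n, or 7.2 at n = 30. Dividing by the per-person variance gives the noncentrality. At ρ = 0.5 this is 7.2/1.00 = 7.2 for change and 7.2/(0.75 × 1.012) = 9.5 for ANCOVA. Power comes from the noncentral F with 2 and 3n − 3 degrees of freedom for change, and 2 and 3n − 4 for ANCOVA. The last column uses the noncentral t. Each cell gives change, then ANCOVA.

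| ρ | Three-group power, 30 per arm | Three-group power, 33.3 per arm | Pairwise difference detectable with 80% power, 30 per arm (SD) |
|---|---|---|---|
| 0.3 | 0.501, 0.691 | 0.548, 0.742 | 0.87, 0.70 |
| 0.5 | 0.652, 0.778 | 0.703, 0.825 | 0.73, 0.64 |
| 0.6 | 0.755, 0.843 | 0.803, 0.883 | 0.65, 0.59 |
| 0.7 | 0.871, 0.918 | 0.906, 0.945 | 0.57, 0.53 |
| 0.8 | 0.970, 0.981 | 0.982, 0.990 | 0.46, 0.44 |

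**Step 4: simulation.** In 20,000 complete-data trials of 30 per arm, the variance ratios were 0.656, 0.761, 0.808, 0.859 and 0.913 in the same order of ρ. Power agreed with step 3 to within 0.003, and both estimators were within 0.003 of the true 0.6.

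**Step 5: unequal SDs.** With k = SD(T2)/SD(T1), the ratio is (1 − ρ²)k² / (1 + k² − 2ρk). The cuts, before and net of slope cost at 30 per arm, are:

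| ρ | k = 0.8: before, net | k = 1.2: before, net |
|---|---|---|
| 0.3 | 50%, 49% | 24%, 23% |
| 0.5 | 43%, 42% | 13%, 12% |
| 0.6 | 40%, 39% | 8%, 7% |
| 0.7 | 37%, 36% | 3%, 2% |
| 0.8 | 36%, 35% | 0%, −1% |

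**The case against.** The planned method is valid, and it matches an aim worded as change from before to after the intervention. The size of the gain rests on a correlation and an SD ratio that the documents do not give, and the 0.6 SD effect is illustrative. At a correlation of 0.8 with equal SDs the gain is small. With a T2 SD 1.2 times the T1 SD, ANCOVA is about 1% worse once the slope is paid for. The instruments are held in a separate file, so it is not shown that each outcome is a continuous score. Aim 2 uses RMANOVA, and changing Aim 1 leaves the two aims with different primary models. Enrolment has already begun.

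Much of this stands as a limit on size. It does not remove the point: in large samples adjustment is never less precise than raw change, and across the range examined the worst case is a loss of about 1% against gains of up to about a third with equal SDs. The aim's wording is no obstacle, since randomisation gives both methods the same target. Different models for Aims 1 and 2 are justified because the Aim 2 caregiver groups are not randomised. The unseen scales and the started enrolment affect how the fix is written.

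If dropout depended on T1 differently by arm, adjustment would also remove a bias from a change analysis of completers. Nothing in the documents predicts that pattern, and the conclusion does not rely on it.

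**Conclusion.** The concern holds. The primary Aim 1 test is an ANOVA on raw change and does not use an available pre-assignment covariate to best effect. The consequence is lost precision, with no bias under randomisation. The loss is material at low to moderate T1–T2 correlation and small at 0.8, and the conclusion is the same for 90 or 100 caregivers. It rests on equal allocation, complete data, continuous outcomes with a common T1 slope across arms and, for the headline range, equal SDs. It covers the questionnaire outcomes only. The documents do not show that heart rate variability is an Aim 1 outcome, and under the remote procedures it is collected by separate arrangement after the T1 session, so its first reading may not precede assignment.

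**What to change.** For Aim 1, make the primary test for each continuous questionnaire outcome an ANCOVA of T2 on T1 by assigned arm, using only T1 values taken before assignment. Keep the three-group, two-wave RMANOVA as a supporting description of change. Leave Aim 2 as it is, because T1 adjustment between non-randomised caregiver groups answers a different question.

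A likelihood model for T1 and T2 with a common T1 mean across arms is an acceptable equivalent. It gains over ANCOVA only from caregivers who have T2 but no T1. Caregivers with T1 only do not inform the arm contrasts under either model: in three simulated trials with 12 to 19 T2 values missing, the contrast with them, without them, and from completer ANCOVA agreed to within 2 × 10⁻⁸.

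The cost is revised analysis text, a different procedure in the same software, one degree of freedom and a common-slope assumption. Because caregivers are already enrolled, the change should be a dated amendment made before outcomes are examined by arm. No extra participants, visits or data are needed.

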PROTOCOL TITLE:

Tailored Health Self-Management Interventions for Highly Distressed Caregivers: Family Members of Persons With Dementia

Identifiers: NCT04247347 Unique Protocol ID: 3R01NR01S817-04S1

PRINCIPAL INVESTIGATOR

[name]

Nursing Science

[contact]

[contact]

Document Date: 6/30/2021

[USE THIS SOCIAL, BEHAVIORAL, AND EDUCATIONAL PROTOCOL TEMPLATE IF YOUR PROJECT INCLUDES SURVEY, INTERVIEWS, FOCUS GROUPS OR EDUCATIONAL RESEARCH ACTIVITIES WITH NO BIOMEDICAL/CLINICAL COMPONENTS]

INSTRUCTIONS:

- Use this template to prepare a document with the information from the following sections.
- Depending on the nature of what you are doing, some sections may not be applicable to your research. If so, please mark as N/A. You may delete contents of sections, but will not be able to delete the headings of the sections.
- When you write a protocol, keep an electronic copy. You will need to modify this copy when making changes.
- Consider using a different color font for your answers.

PROTOCOL TITLE:

Tailored Health Self-Management Interventions for Highly Distressed Caregivers: Family Members of Persons with Dementia

PRINCIPAL INVESTIGATOR

[name]

Nursing Science

[contact]

[contact]

UH FACULTY ADVISOR:

If the principal investigator's primary role at UH is resident, fellow or student, identify a faculty advisor.

N/A

OTHER DEPARTMENTS INVOLVED IN THIS STUDY (IF APPLICABLE):

VERSION NUMBER:

Include the version number of this protocol if assigned by an outside entity.

DATE:

8/7/2019

updated 11/20/19

updated 3/2/20 and 6/29/20

updated 8/19/20

updated 1/6/21 and 4/26/21

updated 6/30/21

Indicate the origin of this protocol (who conceived of and leads the development of the protocol regardless of funding):

- Investigator initiated (*Investigator(s) developed protocol, regardless of funding*)
- Industry (*Pharmaceutical, Device, etc.*) (*Industry developed protocol*)
- Federal (*NIH, DOD, etc.*)
- Cooperative Group (*SWOG, GOG, etc.*)
- Other - *Please specify:*

Funding

Objectives

The AIMS of this supplement are:

- 1. to examine the effectiveness of two health self-management interventions (resourcefulness training and biofeedback) in comparison with usual care (education) on the study outcomes specified in the parent study IRB-2016-1651 (health risks and physical and mental health from pre- to post-intervention) for caregivers of persons with dementia sampled in this supplement;*

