If yes, describe with whom and how the results will be shared.

Aggregated results of the study will be shared with others through manuscripts and presentations.

Study Design/Procedures

Directions: 1) Describe the overall study design. 2) Provide a description of all study-related research procedures being performed, including the length of time involved. 3) Include procedures being performed to monitor research participants for safety or minimize risks. 4) Describe the source records including medical or educational records, which will be used to collect data about subjects.

The proposed 1-year randomized controlled trial will compare the effectiveness of two tailored health self-management interventions (resourcefulness training and biofeedback) with usual care in family caregivers of persons with dementia.

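### Aim 1 compares each intervention with education, but the primary three-group RMANOVA plans no such contrast and does not use T1 as a covariate

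*Combined protocol and SAP*

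**What the plan says.** The Objectives set the two interventions "in comparison with usual care (education) on the study outcomes" of the parent study. Study Design/Procedures repeats that the trial "will compare the effectiveness of two tailored health self-management interventions (resourcefulness training and biofeedback) with usual care". Education is therefore the comparator for both active arms.

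The Data Analysis Plan restates Aim 1 as differences among three groups. "The primary analysis will be a three group × two time waves RMANOVA". It lists effects of time, group and their interaction, and describes the last as "the interaction of time × group, which will allow us to test the trend of the means over time across the three groups". The only contrasts it names run over time, not between groups: "it also uses orthogonal polynomial contrasts to determine linear trends of the means across time". No planned or post hoc comparison of either arm with education appears in the document, and no covariate is mentioned.

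On timing, "Data will be collected at baseline (T1) and within one month after the 4-week intervention (T2"), and "Within two weeks of the first data collection session, caregivers will be randomly assigned using a computer program to one of the three interventions".

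**The concern.** The interaction is the relevant part of the RMANOVA, and the plan's wording suggests it is the intended test. It still answers a different question from Aim 1. It asks whether mean change is the same in all three arms. It does not identify the arm that differs from education or the sign of the difference, and it can be significant because the two interventions differ from each other. The effectiveness claim would then rest on follow-up comparisons chosen after the data are seen, with no error rule.

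A second, lesser matter is precision. T1 enters the model as an outcome wave, so the interaction is an analysis of change. Using T1 as a covariate for T2 estimates the same difference between randomised arms with a smaller standard error.

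The linear-trend sentences are a minor point. With two waves the linear polynomial is the pooled time effect or, by group, the interaction, so it adds no information.

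**Working it through.** **The plan's own figures.** The only derivable figure is the number to screen (Number of Research Participants): 100 / (1 − 0.20) = 125, which reproduces. There is no power calculation to reproduce.

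**Inputs.** Study Design/Procedures refers to 90 caregivers ("All 90 caregivers who receive an intervention or usual care will keep a written log"), which is 30 per arm if allocation is equal. Number of Research Participants gives 100, about 33 per arm. Background calls the pilot effects of resourcefulness training moderate to large, without a number. Assumed here: equal allocation, two-sided 0.05, complete T2 data, one measure with equal SD at both waves, rho 0.3 to 0.7, and an effect of 0.7 SD (0.5 SD also shown).

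**Step 1: what the interaction tests.** With two waves, the time-by-group F equals a one-way F on T2 − T1. A simulated dataset gave 0.6767 both ways. At rho 0.5 the SD of change is √(2(1 − 0.5)) = 1 outcome SD. The omnibus noncentrality is n Σ(mᵢ − m̄)² / SD², on 2 and 87 df.

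| True effects relative to education (SD) | Noncentrality | Omnibus power | Significant omnibus results with neither education contrast below 0.05 |
|---|---|---|---|
| one arm +0.7, other 0 | 9.8 | 79% | 8% |
| one arm −0.7, other 0 | 9.8 | 79% | 8% (by symmetry) |
| both +0.7 | 9.8 | 79% | 0% |
| one +0.35, other −0.35 | 7.35 | 66% | 27% |

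The first three rows have the same power, so the test alone cannot tell one effective arm from one harmful arm or from two effective arms. In the last row each contrast with education has 27% power, and the 27% share in the final column runs from 19% (rho 0.7) to 30% (rho 0.3). The shares come from simulation.

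**Step 2: precision per contrast.** The SD for change is √(2(1 − rho)); for T2 adjusted for T1 it is √(1 − rho²). The variance ratio, adjusted to change, is (1 − rho²) / (2(1 − rho)) = (1 + rho)/2 = 0.65, 0.75 and 0.85 at rho 0.3, 0.5 and 0.7. Power is from the noncentral t with noncentrality d / (SD √(2/n)), on 87 df (change) or 86 df (adjusted).

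| Setting | Change, 0.05 | Adjusted, 0.05 | Change, 0.025 | Adjusted, 0.025 |
|---|---|---|---|---|
| 0.7 SD, rho 0.3, 30 per arm | 62% | 80% | 51% | 71% |
| 0.7 SD, rho 0.5, 30 per arm | 76% | 87% | 67% | 80% |
| 0.7 SD, rho 0.7, 30 per arm | 93% | 96% | 89% | 93% |
| 0.5 SD, rho 0.5, 30 per arm | 48% | 60% | 37% | 49% |
| 0.7 SD, rho 0.5, 24 per arm (20% of T2 missing) | 67% | 79% | 56% | 69% |

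With 33 per arm (0.7 SD, rho 0.5, alpha 0.05) the figures are 80% and 90%. The 95% CI half-width at rho 0.5 and 30 per arm is 0.51 SD for change and 0.44 SD adjusted.

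**Step 3: error rate.** Two uncorrected contrasts with education give about a 9% chance of at least one false positive when no arm differs. By simulation on adjusted T2, Holm brings this to 4.7% and testing only after a significant omnibus group test to 4.2%. With one arm truly effective, the error on the other contrast is 4.3% and 5.1% respectively, so both rules hold close to 5%.

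**The case against.** The strongest reply is that nothing in the planned test is invalid. Aim 1 speaks of outcomes from before to after intervention, and a comparison of change answers that without bias under randomisation. The covariate is a matter of efficiency, and its gain fades as rho rises: 93% against 96% at rho 0.7. The omnibus test is also a reasonable first step (79% power against 76% for one uncorrected change-score contrast at rho 0.5), and education is identifiable as the comparator. On this view the defect is one missing sentence. This stands as to weight: the covariate is the lesser half. It does not remove the gap, because that sentence would be the analysis that answers Aim 1.

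The 27% share needs one arm to be worse than education, which nothing in the documents leads one to expect. That is fair. It is a stress case, and the 8% and 0% cases belong beside it. The 0.7 SD is likewise an assumption, since the pilot statement concerns resourcefulness training only and gives no number.

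The timing of T1 is clear for the questionnaires but less so for heart rate variability. Under the remote procedure in Study Design/Procedures, that measurement is arranged after the T1 session is complete, and randomisation follows within two weeks of that session. Baseline heart rate variability is therefore not guaranteed to precede randomisation. The plan lists it separately from health risks and health outcomes, so the Aim 1 conclusion is unaffected.

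**Conclusion.** The concern holds and should be fixed. The mismatch between Aim 1 and the primary test is plain from the text and depends on no assumption: education is the stated comparator, and no contrast with it is planned. The missing T1 covariate is a loss of precision, not a bias. Under the assumptions above (0.7 SD, 30 per arm, two-sided 0.05) it costs 18 percentage points of power per contrast at rho 0.3 (62% to 80%), 11 at rho 0.5 and 3 at rho 0.7. Error control across the three health outcomes is not part of this point, because those outcomes are defined in a parent study that is not available here.

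**What to change.** For Aim 1, replace the undirected three-group test as the final answer with two planned contrasts, resourcefulness minus education and biofeedback minus education. Estimate each on T2 adjusted for the T1 value and report it with a 95% CI. Control error over the two contrasts within an outcome either by Holm or by testing them only after a significant omnibus group test, which is adequate with three groups. Treat the time and group main effects as descriptive and delete the linear-trend sentences. If heart rate variability is analysed this way, confirm that its baseline was recorded before randomisation.

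The cost is wording in the Data Analysis Plan. T1 and T2 are already collected, and the same participants with both waves are used. The statistical price is lower power from error control. At 0.7 SD, rho 0.5 and 30 per arm, the adjusted contrast falls from 87% to 80% at the strictest Holm step (0.025) or to 84% with the omnibus test first. Both remain above the 76% of an uncorrected change-score contrast; change scores under the same two rules give 67% and 71%. At rho 0.7 there is no net gain over an uncorrected change score: 93% against 93% for the adjusted contrast at 0.025.

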The trajectories of the two conditions differ: caregivers of persons with bipolar disorder experience the fluctuating moods, intensity, and unpredictability of bipolar disorder, caregivers of persons with Alzheimer's disease or related dementias (hereafter referred to as dementia) face a predominantly downward spiral of dementia symptoms and course of illness. Although both groups of caregivers are known to be highly distressed, to date, there are no published comparative studies of caregivers of persons with bipolar disorder and caregivers of persons with dementia. But there is no doubt that both types of caregivers are highly distressed and can benefit from tailored health self-management intervention. The findings from this study have the potential to generate new scientific knowledge about the effectiveness of novel, easy to use, independently performed interventions that can be self-tailored to promote caregiver health through education, biofeedback, or resourcefulness. Once established, these health self-management interventions can be tailored to match the needs and preferences of other comparably distressed family caregivers of persons with other chronic mental or physical conditions.

There are several scientific premises underlying the fundamental assumptions of the proposed study.

- 1. having a family member with any form of dementia is a devastating experience that takes its toll on other family members (i.e., spouses, adult children) who assume responsibility for the care and welfare of the care recipient.*
- 2. The caregiving career follows a long-term trajectory that may last from 4 to 20 years and involves a predictable downward spiral of losses in the care recipient's mental and physical functioning accompanied by changes in the level of care needed.*
- 3. Changes in level of care required to meet the needs of the care recipient over the course of dementia are reflected in a caregiving career comprised of the roles of primary caregiver (in the home) and care partner (with facility placement).*
- 4. Family caregivers are prone to experience stress that can put their own health at risk and adversely affect their physical and mental health over time.*
- 5. Interventions that strengthen a family caregiver's self-management skills will reduce their stress and ultimately sustain their physical and mental health over time.*

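### Aim 2 compares caregivers from two separate studies with an equal-variance test and makes no provision for unequal variances; how much this matters depends on parent-study sizes and SDs that the plan does not give

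*Combined protocol and SAP*

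**What the plan says.** The Data Analysis Plan names Aim 1, the comparison of the three randomised programs among dementia caregivers, as primary. Aim 2 sets "the caregivers of persons with dementia sampled within the proposed administrative supplement with the caregivers of persons with bipolar disorder sampled in the parent study". The method is: "For each intervention/treatment program, a two group by two time point RMANOVA will be used to determine differences within and between groups", together with the time-by-group interaction. It is applied within each of three programs to each of three health outcomes, so there are nine comparisons.

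Randomisation covers program only. In Study Design/Procedures, "caregivers will be randomly assigned using a computer program to one of the three interventions". Whether a person cares for someone with dementia or with bipolar disorder is fixed by which study recruited them.

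On sample size, Number of Research Participants says "we will screen 125 participants to obtain the desired sample of size of 100", while Study Design/Procedures says "All 90 caregivers who receive an intervention or usual care will keep a written log for the 4-week intervention period". The section names no unequal-variance test, group-specific covariance, robust standard error or variance check. It gives no parent-study sample size, no SD of change and no significance level.

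**The concern.** In a standard repeated-measures ANOVA with two groups and two waves, the group-by-time F is the square of the pooled-variance t statistic on change scores. Both groups are taken to share one variance of change. In Aim 1, randomisation from a single population makes that a reasonable start. Aim 2 has no such support, because the two populations were sampled separately, under different studies, in numbers that need not match.

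The equal-variance test tolerates unequal spread when the groups are of similar size. It does not when sizes differ. If the smaller group is the more variable one, the standard error is too small and differences between caregiver types are declared too often. If the larger group is the more variable one, the standard error is too large and real differences are missed.

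**Working it through.** **Plan's own figure.** There is none to reproduce. The documents give no significance level, power, effect size or SD for Aim 2.

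**Inputs.**
- Dementia caregivers per program, n1: 90/3 = 30, or 100/3, about 33, if the allocation is equal. The ratio is not stated, so equal allocation is an assumption. 30 is used below.
- Bipolar caregivers per program, n2: not given. Assumed 30, 60 and 90 to show the range.
- SD of change in each group, s1 and s2: not given. Assumed ratios 1.5 and 2, in both directions.
- Significance level: not given. Two-sided 5% assumed.
- Change scores normal, with no true difference between caregiver types.

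**Step 1: equivalence.** On a simulated data set, the 2x2 interaction F and the squared pooled t on change scores were both 1.1816.

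**Step 2: why size and spread interact.** The pooled test uses, on average,

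E = [((n1-1)s1² + (n2-1)s2²)/(n1+n2-2)] × (1/n1 + 1/n2),

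whereas the true variance of the difference in mean change is V = s1²/n1 + s2²/n2.

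- *Equal sizes (30 and 30, SDs 2 and 1).* E = 2.5 × 2/30 = 0.1667 and V = 4/30 + 1/30 = 0.1667. The ratio E/V is 1 whatever the SDs.
- *30 with SD 2, 60 with SD 1.* Pooled variance = (29×4 + 59×1)/88 = 1.989; E = 1.989 × 0.05 = 0.0994; V = 4/30 + 1/60 = 0.150. E/V = 0.663, so the standard error is √0.663 = 0.814 of what it should be. The critical value 1.987 acts like 1.987 × 0.814 = 1.618, which has a two-sided normal tail of 10.6%.
- *30 with SD 1, 60 with SD 2.* Pooled variance = (29×1 + 59×4)/88 = 3.011; E = 0.1506; V = 1/30 + 4/60 = 0.100. E/V = 1.506, root 1.227. The effective critical value is 2.438 and the tail is 1.5%.

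**Step 3: error rate of the pooled test.** Step 2 is a large-sample approximation. The rates below average the exact conditional rejection probability over 60,000 draws of the two sample variances per cell.

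| Dementia vs bipolar n | SD ratio | Smaller group has larger SD | Larger group has larger SD |
|---|---|---|---|
| 30 vs 30 | up to 2 | 5.0% to 5.2% | (equal sizes) |
| 30 vs 45 | 1.5 | 7.0% | 3.5% |
| 30 vs 60 | 1.25 | 6.9% | 3.5% |
| 30 vs 60 | 1.5 | 8.5% | 2.6% |
| 30 vs 60 | 2 | 11.1% | 1.7% |
| 30 vs 90 | 1.5 | 10.7% | 1.8% |
| 30 vs 90 | 2 | 15.2% | 0.8% |

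If the bipolar group is the smaller one (30 vs 15, SD ratio 2), the rates are 11.2% and 1.8%. With 30 vs 33 they stay between 4.5% and 5.8%. A separate direct simulation (50,000 runs per cell) of the 30, 60 and 90 cases at SD ratios 1.5 and 2 agreed to within about 0.2 of a point.

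**Step 4: the remedy.** The Welch test on change holds 5.0% to 5.1% in every cell of the full grid (n1 30 or 33, n2 15 to 100, SD ratio 0.5 to 2). With equal variances, 30 vs 60 and a true difference of 0.6 SD, power was 75.6% for the pooled test and 75.1% for Welch (100,000 runs).

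**The case against.** The strongest reply is that no defect has been shown. Whether the test misbehaves depends on the parent study's sizes and SDs, which are not in these documents, and with similar group sizes it performs as intended. Aim 2 is a secondary comparison, and a short analysis section that is silent on assumption checks does not prove that none will be made. All of this stands. It is why the point is conditional and minor.

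Three stronger readings are tempting, and the documents do not support them.

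- *That the 5% test in fact runs anywhere from 1% to 15%.* Those ends need roughly a 3:1 imbalance in size together with a 2:1 ratio of SDs. Neither is documented, and unequal sizes and spreads as such do not give that range.
- *That the Background section shows the variances differ.* It says that "caregivers of persons with bipolar disorder experience the fluctuating moods, intensity, and unpredictability of bipolar disorder", while dementia caregivers "face a predominantly downward spiral of dementia symptoms and course of illness". This describes the course of the care recipient's illness. It is not a statement about person-to-person variation in caregivers' health change from T1 to within a month after a 4-week program. If it did imply a larger SD for bipolar caregivers, a larger bipolar group would make the test conservative. Inflation would then require the bipolar group to be the smaller one.
- *That every Aim 2 contrast is affected.* The calculation covers the group-by-time test only. The between-group main effect has a similar weakness, but it depends on the SD of each person's two-visit average, which was not examined. All nine interaction tests would be affected only if spreads differed for every outcome in every program and sizes differed too.

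**Conclusion.** The point holds as a conditional gap in robustness. Aim 2 applies an equal-variance test to two non-randomised, separately sampled populations, without a provision for unequal variances and without the figures a reader would need to rule the problem out. At a moderate imbalance (2:1 in size, 1.5-fold in SD) a nominal 5% interaction test would run at about 2.6% or 8.5%, depending on which group is the more variable. With equal sizes it would run at about 5%.

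These figures rest on 30 dementia caregivers per program, normal change scores, a two-sided 5% level, and assumed parent-study sizes and SDs. The sponsor holds the parent-study data and can settle which case applies. Severity is minor, since the primary aim is unaffected.

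**What to change.** For the Aim 2 group-by-time comparison, specify a Welch test and confidence interval on T1-T2 change. Alternatively, fit a mixed model with a separate covariance matrix for each caregiver type and Satterthwaite or Kenward-Roger degrees of freedom. The mixed model would also cover the between-group main effect, which a Welch test on change does not. It was not simulated here, but is expected to behave much like Welch for the interaction. In either case, state the significance level, and report the number analysed and the SD of change for each caregiver type within each program.

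The cost is a sentence or two in the analysis plan and about half a percentage point of power when the variances are in fact equal. No extra data or staff are needed.
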